Objectives	Primary objective To provide reliable estimates of the effect of trial treatments for each pairwise comparison with the standard care arm on SARS-CoV-2 infection, morbidity and mortality 60 days after randomisation (or appropriate point dependent on the intervention – where this differs to 60 days further detail will be provided in th specific investigational medicinal product (IMP) Appendix).
	Secondary objectives To assess the effects of trial treatments on mortality (all-cause and cause- specific), admission to hospital (all-cause and cause-specific), healthcare referrals for COVID-19, infection (asymptomatic, symptomatic), time to symptomatic infection and safety through serious adverse reactions. To assess the effects of trial treatments on transmission of SARS-CoV-2 infection.
	Tertiary objectives To assess the cost-effectiveness of trial treatments and explain the contextual factors which influence trial processes including adherence to intervention and outcome measurement regimens, and which might impact on subsequent implementations of pre- or post-exposure prophylaxis for COVID-19 in care homes.
Trial Configuration	Overarching platform trial designed to provide reliable evidence on the efficacy of candidate therapies for preventing SARS-CoV-2 infection and transmission in care homes.
Setting	UK Care homes (residential, nursing, mixed).
Sample size estimate comparison of an ac treatment with stan care	tive (around 6,400 residents) is required assuming 1:1 randomisation, two-sided
Trial Prophylactic t name: U1111-1265-4	herapy in care homes trial Protocol Final v1.0 date: 13-May-2021 Page: 7 of 44 068 version:

	variation for care home size 0.49, average number of residents per care home in trial 32, design effect/inflation factor 5.25.					
Number of participants	Each comparison of an active treatment with standard care requires 200 care homes i.e. in the region of a total of 6,400 residents.					
Eligibility criteria	 Care Home criteria Inclusions Location: UK care homes for older people, with and without nursing. Size: ≥20 beds in the care home in total. Exclusions Care Quality Commission quality: Inadequate, or equivalent in devolved administrations. Care Home criteria at treatment phase Exclusions: Positive PCR or lateral flow test (or equivalent) for SARS-CoV-2 in any resident and/or staff within previous 4 weeks 					
	 Resident criteria at trial entry Inclusions Resident in a Care Home. Age ≥65 years Able to give informed consent for participation or a personal legal representative has been identified who can give consent if resident lacks capacity. 					
	 Exclusions: Identified by care home staff to have entered end-stage palliative care. Resident in care home for short-term respite care. Resident's general practitioner is unable to support their involvement in the trial. 					
	 Resident criteria at treatment phase Exclusions: Currently taking all of the trial interventions. Contraindication to all trial interventions - see IMP appendix. In treatment phase of another COVID-19 prevention or treatment trial 					
Description of interventions	Intervention: To be identified by NIHR Prophylaxis Oversight Group (POG) plus standard care. Each intervention will be described within a separate IMP Appendix, each of which will be updated upon confirmation of use within the trial.					
	Comparator: Standard care i.e. no additional intervention.					

Trial	Prophylactic therapy in care homes trial	Protocol Final v1.0	date:	13-May-2021	Page:	8 of 44
name:	U1111-1265-4068	version:				

Randomisation and blinding	 The unit of randomisation is the care home, not the (individual) resident. Allocation concealment will be ensured by enrolling care homes and residents prior to revealing the allocation. There will be no blinding apart from for outcomes sourced from routinely collected health data. Where possible IMP interventions will be open-label. Dynamic randomisation will be employed using a probabilistic minimisation algorithm to balance across important baseline characteristics including: Care home type (residential vs nursing vs nursing and residential) Prior COVID-19 in care home at any time (yes vs no) Size of Care Home - Total number of residents in care home (small (≤30 residents), medium (>30, ≤50 residents), large (>50 residents)) Care home has capacity to give oxygen and/or dexamethasone (yes vs no) Trials of pre-exposure prophylaxis (PEP, i.e. before the care home has a case) and/or post-exposure prophylaxis (PEP, once the care home has a new case to control an outbreak) will be conducted on the platform.
	 For trials of PrEP the care home will be randomised once an IMP has been identified by the NIHR POG and the necessary processes have been implemented. The care home must have had no evidence of SARS-CoV-2 infection for at least 4 weeks. For trials of PEP, care homes will only be randomised once they have an indication of a developing infection, e.g. recent positive PCR or lateral flow test (or equivalent) in a resident or member of staff (index case). The care home must have had no evidence of SARS-CoV-2 infection for at least 4 weeks prior to the index case.
Outcome measures	Primary endpoint:
	 Four-level ordered categorical scale. Participants will be classified according to the highest level, that is, the most serious event they experience during the 60-day period following randomisation: No SARS-CoV-2 infection. SARS-CoV-2 infection but resident remains in care home. Admission to hospital, all-cause. Death, all-cause. SARS-CoV-2 status (positive or negative) will be diagnosed using PCR or lateral flow testing (or equivalent). Secondary endpoints during the 60 days post-randomisation (unless otherwise stated):

Trial	Prophylactic therapy in care homes trial	Protocol Final v1.0	date:	13-May-2021	Page:	9 of 44
name:	U1111-1265-4068	version:				

	 Healthcare referral for COVID-19, e.g. discussion outside of care home with GP (excluding routine visit), 111, 999 paramedic or Emergency Department assessment (without admission), remote hospital consultation. Participant receives dexamethasone in the care home for COVID-19 Participant receives oxygen in the care home for COVID-19 Time to SARS-CoV-2 infection - positive PCR or lateral flow test (or equivalent) (i) with symptoms of COVID-19, (ii) without symptoms of COVID-19, (iii) total i.e. either with or without symptoms of COVID-19. Time to first admission to hospital Cause-specific hospital admission Time to death Days alive and not in hospital Cause-specific mortality, including COVID-19, stroke, pulmonary embolism, myocardial infarction Electronic frailty index at 60 days Ordinal outcome for the most serious event experienced during the 120 days post-randomisation with the following levels: 1. No SARS-CoV-2 infection but resident remains in care home, 3. Admission to hospital, all-cause, 4. Death, all-cause. Safety Serious Adverse Reactions (SAR, excluding primary and secondary outcomes) and Suspected Unexpected SARs (SUSARs). Adverse events relevant to the intervention (see relevant IMP-specific 							
	 Appendix) Clinical – care home level Number of SARS-CoV-2 infections in residents in the care home (aggregate data including residents not participating in PROTECT). Economic evaluation EQ-5D-5L utilities and EQ-VAS at 60 days Quality Adjusted Life Years (QALY) Healthcare resource use and costs Incremental cost-per QALY and Net Monetary Benefit 							
Statistical methods	All comparative analyses will be based on contemporaneously enrolled care homes. The primary approach to between-group comparative analyses will be by intention-to-treat (i.e. according to randomised allocation regardless of adherence to trial allocation). Cluster-level and resident-level descriptive statistics will be used to illustrate balance between the groups at baseline. Primary comparative analyses will employ a multi-level ordinal logistic regression model with a random effect to account for clustering within care homes. The model will adjust for characteristics used in balancing random allocation between treatment arms and individual-level characteristics of age, sex, and vaccination status.							
TrialProphylactic therapy in uname:U1111-1265-4068	care homes trial Protocol Final v1.0 date: 13-May-2021 Page: 10 of 44 version:							

TABLE OF CONTENTS

Contents

1.1. Background

In 2019 a novel coronavirus-induced disease (COVID-19) emerged in Wuhan, China. A month later the Chinese Center for Disease Control and Prevention identified a new beta- coronavirus (SARS coronavirus 2, or SARS-CoV-2) as the aetiological agent.1 Subsequently, the disease has spread around the world infecting more than 132 million people and causing more than 2.8 million deaths (https://www.arcgis.com/apps/opsdashboard/index.html#/bda7594740fd40299423467b48e9ecf6). Viral infection may be asymptomatic or present, typically, with fever, fatigue, cough and anosmia. In a minority of people, COVID-19 develops into a serious or fatal disease presenting with viral pneumonitis causing respiratory failure, cerebral infarction causing stroke, pulmonary embolism, or myocardial infarction causing heart failure; these requiring hospitalisations and for some, admission to an intensive care unit for ventilation. The progression of disease from mild symptoms to hospitalisation to death typically takes 2 weeks for each transition. Risk factors for a poor outcome include increasing age, non-white ethnicity and the presence of co-morbidities such as obesity and diabetes. Beyond public health measures to prevent infection (hygiene, masks, personal protective equipment, maintaining distance), we urgently need treatments to minimise these direct and indirect impacts on residents. One treatment, dexamethasone, reduced COVID-19 deaths in hospitalised patients with severe disease and needing oxygen therapy.[1] No other interventions are known to alter outcome. Symptomatic disease may be prevented with some (e.g. Pfizer, Moderna and AstraZeneca/University of Oxford) but not all (CSL/University of Queensland) vaccines, and a massive world-wide effort is currently underway to offer vaccination.

The COVID-19 pandemic has had a catastrophic effect in care homes with direct effects through causing illness and death, and indirect impact from policies to reduce viral spread into care homes, e.g. by limiting family visits. Vaccination against SARS-CoV-2 has commenced in care homes but its efficacy in older people with multiple comorbidities and immunosenescence remains poorly defined. Hence, there is an urgent need for additional prophylactic interventions to protect Care Home residents.

1.2. Trial Rationale and Risk/Benefit Assessment

Vaccines are intended to and usually prevent symptomatic COVID-19 disease (and in some cases reduce disease severity), however, vaccines may be less effective in older people with immunosenescence so there is an additional need for effective prevention strategies in Care Home residents, a group who are at high risk of infection and poor outcomes.

The case fatality rate (95% CI) for care home residents with COVID-19 during the first wave of the pandemic in 2020 was 35.7% (31.9-39.7%). Importantly care home residents with no direct evidence of infection of COVID-19, were twice as likely to die if their home experienced an outbreak, than if they lived in a home with no COVID-19.³⁰

Coming forward to 2021. The VIVALDI-2 study considered 10,412 residents (median age 86 years) from 310 care homes, 9,160 were vaccinated with either ChAdOx1 (6,138; 67%) or BNT162b2 (3,022; 33%) vaccines. A total of 670,628 person days and 1,335 PCR-positive infections were included. Adjusted hazard ratios (aHRs) for PCR-positive infection relative to unvaccinated residents declined from 28 days following the first vaccine dose to 0.44 (0.24, 0.81) at 28-34 days and 0.38 (0.19, 0.77) at 35-48 days. Similar effect sizes were seen for ChAdOx1 (aHR 0.32 [0.15-0.66] and BNT162b2 (aHR 0.35 [0.17, 0.71]) vaccines at 35-48 days.²⁹

Trial	Prophylactic therapy in care homes trial	Protocol Final v1.0	date:	13-May-2021	Page:	15 of 44
name:	U1111-1265-4068	version:				

Vaccination diminishes the risk of COVID-19 infection for care home residents but does not remove it completely. COVID-19 infection is associated with high mortality for all residents who live in a care home where an outbreak becomes established. If prophylactic therapies can modify the transmission and severity of SARS-CoV-2 infection, then they will be of substantial benefit to residents throughout the care home. Importantly, both agents being considered at present are postexposure prophylaxis. By the time a resident starts taking one of the study medications, they are at increased risk of dying by virtue of exposure.

1.2.1. Justification for participant population/setting

Residents of Care Homes are at both high risk of contracting SARS-CoV-2 and of developing severe disease and dying. In the UK, approximately one-third of deaths occurring during the first wave of infection (March-June 2020) took place in Care Homes. Despite the vaccination programme care home residents remain vulnerable to contracting SARS-CoV-2 due to underlying co-morbidities and possible immunosenescence.

1.2.2. Justification for design

The design uses a platform structure that allows multiple treatments to be evaluated simultaneously. Randomisation will use equal probability between all active treatments in a comparison group and a single standard care arm (i.e. allocation ratio 1:1:1:1 if three experimental treatments are in the trial concurrently) and all comparative analyses will be based on

Trial	Prophylactic therapy in care homes trial	Protocol Final v1.0	date:	13-May-2021	Page:	16 of 44
name:	U1111-1265-4068	version:				

contemporaneously enrolled care homes. To ensure that the platform delivers answers on whether treatments are effective in prevention in a timely manner, the number of active treatments will be limited to three at most at any point. This is to ensure that a sufficient number of care homes can be recruited to the platform as well as limiting the duration required to determine an answer for each intervention. Trials of pre-exposure prophylaxis (PrEP, i.e. before the care home has a case) and post-exposure prophylaxis (PEP, once the care home has a new case to control an outbreak) will be conducted on the platform.

New treatments will be added to the platform by recruiting additional care homes or re-randomising previously enrolled care homes that have completed follow up and provided that the prophylactic effect of the previous treatment is expected to have washed-out (which will be quick for some candidate drugs, but likely up to 6 months for synthetic antibody treatments). These care homes will subsequently be randomised 1:1 between active and standard care using dynamic allocation. When a new potential treatment is to be included in the platform, it will be added immediately provided that no more than two active treatments are already in the platform. If the trial is already investigating three active treatments, then inclusion of a new treatment in the platform will be delayed until the target number of participants have been randomised in one of the current treatment comparisons.

Any platform trial design needs to be adaptable to fit the interventions being tested. This is compounded by specific issues of relevance to care home research, in particular a relative lack of research experience and capacity; a high proportion of participants who lack capacity to consent (up to 76%);[2] delivery, storage and administration of interventions; collection of outcomes by care assistants; and variable care practices and resourcing within care homes. Our platform is designed to account for these:

- Pragmatic adaptive cluster-randomised parallel group platform design. This allows multiple agents to be compared simultaneously, and with new agents added once existing ones have been tested and shown to be beneficial or futile. Treatments may also be tested in combination, if appropriate.
- Cluster randomisation. Cluster designs are particularly relevant to care home trials since they reduce the risk of bias due to contamination,[3] facilitate recruitment and drug management and delivery, and ease identification of serious adverse events. Further, they likely reflect the manner that prophylactic agents will be used in care homes, i.e. for all residents able/willing to take treatment.
- Randomisation of care homes without current infection, and care homes with new outbreaks, as appropriate to the treatment being evaluated, i.e. a mix of pre- and post-exposure prophylaxis.
- The comparator is expected to be standard care. This approach has pros and cons, but we will use a PROBE design in PROTECT-CH (as in the RECOVERY, PRINCIPLE, ATOMIC2, and AVID-CC trials); placebo will be considered on a case-by-case basis depending on the IMP.
- Interventions may vary in what primary outcome is most appropriate, so the platform can
 accommodate different primary outcomes for different interventions (all outcomes will be
 recorded in all participants). For the purpose of this platform, we have chosen an ordinal
 outcome following the WHO recommendation to use ordinal outcomes in COVID-19 trials.[4, 5]

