The resident's decision to participate in the trial or not should be recorded in their care home records. Ideally this will include date of discussion, the name of the trial, summary of discussion, version number of the Participant Information Sheet (PIS) given to participant and a copy of the ICF signed and date consent received (if completed on paper).

Contact details of the research team will be provided to participants/personal legal representatives should they have any questions about their ongoing participation in the trial. Any new information that may be relevant to their continued participation will be provided. Where new information becomes available which may affect the participants' decision to continue, they will be given time to consider and if happy to continue will be re-consented. Re-consent will be documented in the care home notes. Should an additional treatment be added to the platform, information will be provided to the resident and they will be re-consented and eligibility re-confirmed. The participant's right to withdraw from the trial will remain.

For residents who lack capacity

The above process will be followed except that a personal legal representative identified by the care home as responsible for decisions about the resident's care will be asked to give consent on behalf of the resident. Care home staff will seek permission from personal legal representatives for

Trial	Prophylactic therapy in care homes trial	Protocol Final v1.0	date:	13-May-2021	Page:	23 of 44
name:	U1111-1265-4068	version:				

collection and storage of their contact details to enable the research team to contact them regarding a resident's participation in the trial. Minimal identifying details about the resident will also be collected with their permission to facilitate the consenting process. If a personal legal representative cannot be identified the resident will not be recruited into the trial. A personal Legal Representative Information Sheet (LIS) will be provided to facilitate this process. The legal representative will be given time to read the LIS and to discuss participation with others (i.e. family members, GP or other healthcare professionals outside of the site research team, if they wish). The personal legal representative will give explicit consent for the regulatory authorities, members of the research team and representatives of the Sponsor to be given direct access to the participant's medical records.

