6.2. Randomisation

The unit of randomisation is the care home (cluster). The allocation for a particular care home will only be revealed following the screening of residents for eligibility, gaining informed consent and collection of baseline data. The randomisation programme will allocate care homes 1:1 to each available treatment arm or standard care arm.

Care homes will be randomised via a secure password-protected website created and maintained by Nottingham Clinical Trials Unit. The dynamic randomisation will use a probabilistic minimisation algorithm to ensure balance across:

- Care home type (residential vs nursing vs nursing and residential)
- Prior COVID-19 in care home at any time (yes vs no)
- Size of Care Home Total number of residents in care home (small (<30 residents), medium (>30, <50 residents), large (>50 residents))
- Care home has capacity to give oxygen and/or dexamethasone (yes vs no)

Trial	Prophylactic therapy in care homes trial	Protocol	Final v1.0	date:	13-May-2021	Page:	24 of 44
name:	U1111-1265-4068	version:					

The NCTU will confirm that all checks required for "green light" of a care home for randomisation have been completed. Randomisation will then be carried out by the PI (or delegated investigator) using a remote, internet-based randomisation system to obtain the treatment allocation for each care home after confirmation of care home participation, and consent and eligibility checks for the residents.

For trials of PrEP the care home will be randomised once an IMP has been identified by the NIHR POG and the necessary processes have been implemented.

For trials of PEP the care home will be randomised once an IMP has been identified by the NIHR POG and the necessary processes have been implemented and a resident or member of staff in the care home has tested positive for SARS-CoV-2 (PCR or lateral flow test, or equivalent).

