13.2. Analysis of Outcome Measures

Statistical analyses

The analysis and reporting of the trial will be in accordance with CONSORT guidelines for adaptive and cluster designs [14, 15] with the primary comparative analyses being conducted according to randomised allocation with due emphasis on confidence intervals for between-arm comparisons. All comparative analyses will be based on contemporaneously randomised care homes. A full statistical analysis plan will be developed and agreed with the Platform Steering Committee (PSC) prior to the first release of treatment allocations for final pairwise comparison. The primary approach to between-group comparative analyses will be by intention-to-treat (i.e. according to randomised allocation regardless of adherence to trial allocation). Cluster-level and resident-level descriptive statistics will be used to illustrate balance between the groups at baseline.

Trial	Prophylactic therapy in care homes trial	Protocol	Final v1.0	date:	13-May-2021	Page:	35 of 44
name:	U1111-1265-4068	version:					

Primary comparative analyses will employ a multi-level ordinal logistic regression model including all residents eligible for the intervention of interest prior to care home randomisation. The model will adjust for the minimisation factors, plus the individual-level covariates age, sex and vaccination status. A random effect to adjust for clustering within care homes will be used. The treatment comparison will be presented as an adjusted common odds ratio for a shift in the direction of a better outcome on the ordinal scale together with 95% confidence intervals.[16-19]

Secondary outcomes will be analysed using appropriate regression models dependent on data type (binary, categorical, continuous, time to event etc.), adjusted similarly and accounting for clustering within care homes.

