4.2. Analysis sets

Outcome	Analysis set
Primary, secondary and safety outcomes – individual-level	Contemporaneously randomised care homes and their eligible residents analysed according to the group their care home was randomly allocated to regardless of adherence to trial allocation (Intention-to-treat [ITT] analysis population).
	Since not all residents will be eligible for all trial interventions, residents in homes allocated to standard care will only be included in a given comparison if they were eligible to be given the intervention of interest had their home been randomised to it (i.e. not taking the intervention of interest, or another drug in the same class, and did not have any contraindications to it).
	In the case where an outbreak based on a positive result from a lateral flow test is not confirmed with a PCR test, then the site remains in the trial in the ITT analysis population.
	Primary analysis will be for participants with complete outcome data collected (i.e., without imputation for missing data).
Care home level infection rate	All residents in contemporaneously randomised care homes including residents not consenting to PROTECT-CH included in the comparison.

Outcome	Analysis set		
Supplementary analyses (for	All residents with consent regardless of whether		
primary outcome and the	eligible/took part in treatment phase of trial, analysed according to the group their care home was randomly allocated.		
secondary outcome related to			
transmission (time to SARS-			
CoV2 infection))			

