7. ANALYSIS OF EFFECTIVENESS

The analysis and reporting of the trial will be in accordance with CONSORT guidelines for cluster[7] and adaptive[8] designs. Analyses will be based on pairwise comparisons between each treatment arm and the concurrent standard care arm (reference group). Primary comparative analyses will be based on intention-to-treat principle, with all care homes and residents (eligible for the intervention prior to randomisation) within these care homes analysed according to treatment to which the care home was randomised. All tests will be two-tailed with point estimates and 95% confidence intervals for the treatment effect presented. No formal adjustment for multiple significance testing will be applied [9]. Secondary outcomes will be considered supportive to the primary outcome.

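### The analysis set does not require that a standard-care home could have been allocated the treatment it is compared with, so homes added for a new treatment could become non-randomised controls for older ones

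*Protocol*

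**What the plan says.** **Who the controls are.** Protocol 13.2: "All comparative analyses will be based on contemporaneously randomised care homes". SAP 4.2 defines the individual-level analysis set as "Contemporaneously randomised care homes and their eligible residents analysed according to the group their care home was randomly allocated to". SAP 7 likewise compares each arm with the concurrent standard care arm. The only further filter works at resident level: Protocol 4.2 and SAP 4.2 drop residents who were already taking the drug (or one of its class) or had a contraindication to it. Protocol 13.6 speaks of the standard care arm corresponding to each treatment but does not define it.

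**How homes are allocated.** The texts differ.

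- Protocol 1.2.2, general rule: "Randomisation will use equal probability between all active treatments in a comparison group and a single standard care arm", with 1:1:1:1 given as the case of three concurrent treatments. The term for a group of compared treatments is not defined.
- Protocol 1.2.2, later: "New treatments will be added to the platform by recruiting additional care homes or re-randomising previously enrolled care homes that have completed follow up", subject to wash-out, and then "These care homes will subsequently be randomised 1:1 between active and standard care using dynamic allocation".
- Protocol 6.2: "The randomisation programme will allocate care homes 1:1 to each available treatment arm or standard care arm".

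A new treatment may join at once if no more than two active treatments are open (Protocol 1.2.2), so overlap between old and new comparisons is expected.

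**The concern.** A control home gives an unbiased comparison with treatment A if, when it was randomised, it could have been given A. Being randomised in the same weeks is not enough. Suppose A is open, B is added, and the homes brought in for B are randomised only between B and standard care. Their standard-care homes run alongside A's and meet the wording of SAP 4.2 for A's comparison, yet they had no chance of receiving A. They are also a distinct group: late recruits, or homes that have already completed one comparison.

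The primary model adjusts for the minimisation factors, age, sex and vaccination status (SAP 7.1). It has no term for recruitment stream, so any remaining difference in baseline risk between streams passes into the common odds ratio for A.

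**Working it through.** **1. Which allocation text applies.**

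| Reading | Source | Could a standard-care home be a control for a treatment it could not have received? |
|---|---|---|
| One list of all open arms | 1:1:1:1 rule in 1.2.2; 6.2 | No, within that list |
| Separate 1:1 stream for each added treatment | Sentence on added homes in 1.2.2 | Yes, unless the analysis set excludes it; SAP 4.2 does not |

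**2. The plan's own sample size (Protocol 13.1, SAP 2.1).** Inputs: standard-care distribution 60/15/10/15%, two-sided 5%, power 90%, ICC 0.11, CV 0.49, 32 residents per home.

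- Whitehead: n per group = 6(1.96 + 1.2816)² / [(ln OR)²(1 − Σp̄³)], with p̄ the mean category proportions of the two arms. OR 2/3 gives 529.06, so 530 as stated. OR 0.67 gives 542, within 2.2%.
- Design effect = 1 + [(0.49² + 1) × 32 − 1] × 0.11 = 5.255 (stated 5.25).
- Homes = 2 × 530 × 5.25 / 32 = 173.9 (stated 174, raised to 200).

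These figures reproduce. The platform total depends on the reading:

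- One list of four arms: 4 × 100 = 400 homes, 12,800 residents. This is the plan's total.
- Three separate 1:1 streams, each with its own controls: 3 × 200 = 600 homes, 19,200 residents.
- Partial overlap lies between the two.

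**3. Illustrative bias.** Two inputs are assumptions found in neither document: r, the odds of a worse outcome in the added stream relative to the other homes, and w, the added stream's share of the controls. Read r as the difference left after covariate adjustment.

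For r = 0.7, dividing each cumulative odds of the better categories by r changes 60/15/10/15% to 68.2/12.9/7.9/11.0%. With w = 0.5 the pooled control is 64.1/13.9/9.0/13.0%. A treatment with no effect stays at 60/15/10/15%. At the first cut the odds ratio for a worse outcome is (0.6409/0.3591) / (0.60/0.40) = 1.19. A proportional-odds fit over all three cuts also gives 1.19.

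| r | w | True OR 1 appears as | True OR 0.67 appears as |
|---|---|---|---|
| 0.7 | 0.50 | 1.19 | 0.80 |
| 0.7 | 0.25 | 1.09 | 0.73 |
| 0.8 | 0.50 | 1.12 | 0.75 |
| 1.25 | 0.50 | 0.89 | 0.60 |
| 1 | 0.50 | 1.00 | 0.67 |

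**4. Illustrative type I error.** Assume A has 100 homes and 100 controls of its own, and 100 control homes are pooled in from the other stream. Bias on the log scale ≈ w ln r. SE = √[3(n₁ + n₀) / (n₁n₀(1 − Σp̄³))], with n₁ = 100 × 32 / 5.255, n₀ = 200 × 32 / 5.255 and 1 − Σp̄³ = 0.7255, which gives 0.1009. For r = 1.25 the bias is 0.5 × 0.2231 = 0.1116, and the two-sided error is Φ(0.1116/0.1009 − 1.96) + Φ(−0.1116/0.1009 − 1.96) = 19.7% on unrounded values. For r = 1.10 it is 7.6%, and for r = 1.50 it is 51.9%.

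**The case against.** The strongest reply is that the plan intends one common list. Protocol 6.2 is the operative randomisation section and applies its 1:1 ratio to every available arm, so the same ratio in 1.2.2 may be loose shorthand. The 400-home total for three treatments assumes one shared control. Protocol 5 adds: "Should an additional treatment be added to the platform, information will be provided to the resident and they will be re-consented and eligibility re-confirmed". That suggests enrolled homes can be allocated a later drug. On such a list the problem does not arise. This stands, and it is why the point is conditional. A reader might infer that added homes are certain to be randomised only against standard care and certain to be pooled into older comparisons. The documents do not support that: they conflict on allocation, and nowhere order pooling across streams. Equally, nothing in them prevents it.

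The bias figures are also fairly challenged. The stream differences are assumed, their direction is unknown, all homes meet the same entry criteria, and adjustment may remove part of any difference.

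Two further inferences go too far.

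- **That PrEP and PEP controls will be pooled.** The documents describe these as separate trials with incompatible triggers for randomisation. They do not say that the controls are kept apart, but neither do they combine them.
- **That residents not re-consented for a later drug break the comparison.** Protocol 4.2 and 13.2 and SAP 7 already limit the analysis to residents eligible for the intervention before randomisation. Any remainder is expected equally in both arms, which is ordinary intention-to-treat dilution.

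**Conclusion.** The gap is real but conditional. Controls are defined by timing and resident-level drug eligibility, with no rule at home level, and the protocol gives two incompatible accounts of how added homes are allocated. Under the separate-stream account, the stated analysis set lets homes that were never randomised against a treatment serve as its controls. Under the common-list account it does not.

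The size cannot be known from the documents. It is zero if the streams have equal baseline risk. The range of 1.19 to 0.89 for a null treatment rests on assumed residual relative odds of 0.7 to 1.25 in half the controls, and shows only that a moderate difference would matter against a target odds ratio of 0.67. The sample-size arithmetic is not in error, but the 400-home total holds only under a single shared list.

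**What to change.** 1. Reconcile Protocol 1.2.2 with 6.2: state the set of arms open to an additional or re-randomised home when other treatments are running, and define the group of treatments that share a standard care arm.
2. In Protocol 13.2 and SAP 4.2, state: *a home enters the comparison for treatment X only if X was one of its possible allocations at the moment it was randomised, and it was allocated to X or to standard care.* This also keeps PrEP and PEP controls apart without a separate rule. The existing resident-level eligibility filter stays as it is.
3. Record the set of open arms with each allocation in the randomisation system, so that the rule can be applied from data and not reconstructed later.

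The cost is wording in two documents and one stored field. Some comparisons may have fewer control homes than selection by date alone would give. If separate 1:1 streams are intended, the platform total for three treatments needs restating, up to 600 homes.
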